- Mean change from Randomization (Week 12) to Week 24 in the YGTSS-TTS for ecopipam compared to placebo.
- Mean change from Randomization (Week 12) to Week 24 in the Clinical Global Impression of Tourette Syndrome Severity (CGI-TS-S) for ecopipam compared to placebo.
- Mean change from Randomization (Week 12) to Week 24 in the YGTSS-Global Severity (GS) score for ecopipam compared to placebo.
- Mean change from Randomization (Week 12) to Week 24 in the Caregiver Global Impression of Change (CaGI-C) for ecopipam compared to placebo.
- Time from Randomization (Week 12) to a loss of ≥ 50% of the improvement from Baseline (Day 1) experienced on the Yale Global Tic Severity Scale- Total Tic Score (YGTSS-TTS) at the last visit (Week 12) in the open-label Stabilization period.
- Mean change from Randomization (Week 12) to Week 24 in the Clinical Global Impression of Tourette Syndrome Improvement (CGI-TS-I) for ecopipam compared to placebo.
- Mean change from Randomization (Week 12) to Week 24 in the Premonitory Urge for Tics Scale (PUTS) for ecopipam compared to placebo.
- Mean change from Baseline (Day 1) to Week 24 in Gill s de la Tourette Syndrome—Quality
 of Life Scale for Children and Adolescents (C&A-GTS-QOL) score for ecopipam compared
 to placebo.
- Mean change from Baseline (Day 1) to Week 24 in Gilles de la Tourette Syndrome–Quality of Life Scale (GTS-QOL) score in adults f r ecopipam compared to placebo.
- Mean change from Baseline (Day 1) to Week 12 in the YGTSS-TTS.
- Percentage of subjects with a decrease in their YGTSS-TTS by 25% or greater at any time point from Baseline (Day 1) to Week 12.
- Mean change from Baseline (D y 1) to Week 24 in the YGTSS-TTS for ecopipam compared to placebo.
- Mean change from Baselin (Day 1) to Week 24 in the YGTSS-GS score for ecopipam compared to placebo
- Mean change from Baseline (Day 1) to Week 24 in the Clinical Global Impression of Tourette Syndrome Severity (CGI-TS-S) for ecopipam compared to placebo.
- Caregiver Global Impression of Change (CaGI-C) through Week 24 for ecopipam compared to placebo.
- Mean change from Randomization (Week 12) to Week 24 in the Gilles de la Tourette Syndrome–Quality of Life Scale for Children and Adolescents (C&A-GTS-QOL) for ecopipam compared to placebo.
- Mean change from Baseline (Day 1) to Week 24 in the Clinical Global Impression of Tourette Syndrome Improvement (CGI-TS-I) for ecopipam compared to placebo.

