13.4. Planned Analysis

13.4.1. Efficacy Analysis

The primary efficacy endpoint is time from Randomization to Relapse defined as a loss of $\geq 50\%$ of the improvement experienced on the YGTSS-TTS at the last visit in the open-label Stabilization period (Week 12), or initiation of additional medications to treat symptoms of TD, or requirement of hospitalization for w rsening symptoms of TD in subjects ≥ 6 and < 18 years during the double-blind R/WD period for ecopipam compared to placebo. Data from subjects who complete or discontinue from the double-blind R/WD period without Relapse will be considered as censored obs rvations. The log rank test will be the primary test of statistical significance. Kaplan-Meier curves will be used to compare the times to relapse between the treatment groups. The hazard ratio and its 95% confidence interval (CI) will be estimated from the Cox proportional hazard model with treatment as a factor. The proportional hazards assumption will be evaluated graphically and analytically, for example by assessing martingale and Schoenfeld residuals and by modeling time-dependent covariates. The analysis of the primary efficacy endpoint will be performed in the mITT and PP populations according to the randomized treatment. Details will be provided in the Statistical Analysis Plan.

The time-to-event secondary and exploratory endpoints related to Relapse will be analyzed in a similar manner as the primary endpoint. The exploratory endpoints of mean change will be assessed with a Mixed Model for Repeated Measures (MMRM) model using the SAS MIXED procedure, with a REPEATED statement, with no imputation. The model will include fixed effects for treatment, visit, the interaction between treatment and visit, and a covariate for baseline score for the given assessment and other covariates such as gender, age group, race/ethnicity, and region. All secondary and exploratory endpoints will be analyzed in the mITT population according to randomized treatment. Details will be provided in the Statistical Analysis Plan.

Protocol EBS-101-TD-301 Version 9.0, 05 March 2024

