### 8.2. Key Definitions and Derivations

Treatment emergent adverse events (TEAEs) are defined as any adverse events that start or increase in intensity on or after the first dose of treatment on Day 1.

Timing-specific adverse events are defined as any adverse events that occur or increase in intensity during any specifically defined study milestones: open-label stabilization period (OLAE), double-blind R/WD phase (RWDAE), taper down (TDAE) and off study drug (ODAE).

Prior medications are defined as medications entered in the eCRF that either start, or end before the first dose of study medication. Concomitant medications are defined as medication on the eCRF that are taken on or after or are ongoing at the start date of dosing.

Duration of exposure (days) to study drug is defined as (Date of Last Dose – Date of First Dose) +1. If the date of last dose is unknown, then the date of last clinical visit will be used to impute the date of last dose.

Baseline is defined as the last measurement taken before the first dose of ecopipam in the open-label stabilization period.

Change from baseline will be calculated for the post-baseline assessments as post-baseline value – baseline value. Similarly, change from randomization will be calculated for the post-randomization assessments as post-randomization value – randomization value.

Demographics and baseline characteristics will be derived as follows:

Age at Study Day 1 = (Study day 1 visit date - date of birth + 1) / 365.25 and truncated to complete years.

Height (in cm) = height (in inches) \* 2.54

This document is confidential.

SAP text Version: SAP text 3.0 6-Dec-2023

Controlled Document ID: 3903A.02, Effective Date 31-Aug-2020

Weight (in kg) = weight (in lbs) \* 0.4536

BMI (kg/m2) = Weight(kg)/[Height(m)2]

To calculate weight, height and BMI z-scores for children and adolescents, Centers for Disease Control and Prevention (CDC) growth charts will be used (see section 13)

For adults, weight, height and BMI z-scores will be calculated as follows:

(Weight, Height and BMI) z-scores = (Weight, Height and BMI) - mean (Weight, Height and BMI) of all subjects at the baseline visit/ Standard deviation of (Weight, Height and BMI) of all subjects at the baseline visit.

Treatment compliance, as a percentage, will be derived on the eCRF as follows:

Treatment compliance (%) = Actual Tablets Used\*100/Expected Tablets Used

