The mean change from Randomization (Week 12) to Week 24 (Weeks 13,14,15,16,18,20, 22 and 24) in YGTSS-TTS will be summarized. This endpoint will be analyzed with a Mixed Model for Repeated Measures (MMRM) model using the SAS MIXED procedure with REPEATED statement. The model with an unstructured covariance matrix will include fixed effects for treatment, visit, interaction between treatment and visit, region, age group (0 = children 6-11, 1 = adolescents 12-17, 2=adults >=18) and covariate for week 12 YGTSS-TTS. Visit will include weeks 13,14,15,16,18, 20, 22 and 24. By visit comparisons will be provided. In the event the model does not converge using the standard unstructured covariance matrix, the Fisher scoring algorithm to obtain initial values of covariance parameters will be tried. If this method fails to converge, the FA0(T) structure will be tried. Following failure of this method, the successive univariate method proposed by Lu and Mehrotra (2010) will be tried. In the event all the previous methods fail to converge, the autoregressive and Toeplitz structures will be tried, and a sandwich estimator for the treatment effect estimate will be implemented. The final covariance structure will be documented in the table. All observed endpoint data will be used in this analysis, without imputation.

Summary statistics will be presented along with a full data listing by treatment group.

10.2.5. Mean change from Randomization (Week 12) to Week 24 in the CGI-TS-S for ecopipam compared to placebo.

An exploratory analysis will be performed on the change in CGI-TS-S from randomization to Week 24.

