# Statistical analysis:

The mean change from Randomization (Week 12) to Week 24 (Weeks 13,14,15,16,18,20, 22 and 24) in CGI-TS-S will be summarized. This endpoint will be analyzed with a Mixed Model for Repeated Measures (MMRM) model using the SAS MIXED procedure with REPEATED statement. The model with an unstructured covariance matrix will include fixed effects for treatment, visit, interaction between treatment and visit, region, age group (0 = children 6-11, 1 = adolescents 12-17, 2=adults >=18) and covariate for week 12 CGI-TS-S. Visit will include weeks 13,14,15,16,18,20, 22 and 24. By visit comparisons will be provided. In the event the model does not converge using the unstructured covariance matrix, the methods described in Section 10.2.4 will be tried. The final covariance structure will be documented in the table. All observed endpoint data will be used in this analysis, without imputation. Summary statistics will be presented along with a full data listing by treatment group.

10.2.6. Mean change from Randomization (Week 12) to Week 24 in the YGTSS-Global Severity (GS) Score for ecopipam compared to placebo.

An exploratory analysis will be performed on the change in YGTSS-Global score (GS) from randomization to Week 24.

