### Statistical analysis:

The analysis method for the YGTSS-TTS will be analyzed with a Mixed Model for Repeated Measures (MMRM) model using the SAS MIXED procedure with REPEATED statement. The model with an unstructured covariance matrix will include fixed effects for treatment, visit, interaction between treatment and visit, region, age group (0 = children 6-11, 1 = adolescents 12-17, 2=adults >=18) and covariate for baseline YGTSS-TTS. Visit will include weeks 4, 8, 12, 13,14,15,16,18,20, 22 and 24. By visit comparisons will be provided. In the event the model does not converge using the unstructured covariance matrix, the methods described in Section 10.2.4 will be tried. The final covariance structure will be documented in the table. All observed endpoint data will be used in this analysis, without imputation.

Summary statistics will be presented along with a full data listing by treatment group.

10.2.16. Mean change from Baseline (Day 1) to Week 24 in the YGTSS-GS for ecopipam compared to placebo.

See section 10.1 for a description of the YGTSS-GS. An exploratory analysis will be performed on the change in YGTSS-TTS from Baseline to Week 24 (Weeks 4, 8, 12, 13, 14, 15, 16, 18, 20, 22 and 24).

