# 14. Changes from Analysis Planned in Protocol

There are no changes from the analysis planned in protocol.

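### The SAP models for change from Randomization to Week 24 adjust for the Week 12 score but leave out the Day 1 score of the same scale, which could be added at almost no cost for a nil-to-modest gain

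*Protocol*

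**What the plan says.** The protocol synopsis lists exploratory endpoints such as "Mean change from Randomization (Week 12) to Week 24 in the YGTSS-TTS for ecopipam compared to placebo". For this one, SAP 10.2.4 fits a repeated-measures model with treatment, visit, their interaction, region, age group and a "covariate for week 12 YGTSS-TTS. Visit will include weeks 13,14,15,16,18, 20, 22 and 24". SAP 10.2.5 has the same structure, with a "covariate for week 12 CGI-TS-S", as do 10.2.6 (YGTSS-GS), 10.2.10 (PUTS), 10.2.19 (C&A-GTS-QOL, a single time point) and 10.2.23 (YGTSS subscales). None includes the Day 1 score. The models for change from Day 1 use the Day 1 score instead; 10.2.15, for example, has a "covariate for baseline YGTSS-TTS".

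Protocol 13.4.1 covers all mean-change endpoints in one sentence, naming "a covariate for baseline score for the given assessment and other covariates such as gender, age group, race/ethnicity, and region", and leaves details to the SAP. SAP 8.2 states: "Baseline is defined as the last measurement taken before the first dose of ecopipam in the open-label stabilization period". SAP 14 states: "There are no changes from the analysis planned in protocol".

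The Schedule of Assessments collects YGTSS, CGI-TS-S, PUTS and C&A-GTS-QOL at Day 1. It schedules no Day 1 value for CaGI-C or CGI-TS-I. (SAP 10.2.2 does list a Baseline CGI-TS-I, against the schedule.)

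**The concern.** These endpoints measure worsening after drug is withdrawn. Week 12 is where a subject starts; Day 1 is the untreated level to which the subject may return. If placebo subjects drift back toward Day 1, two subjects with the same Week 12 score have different expected worsening, and a model without Day 1 leaves that difference in the residual variance.

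The second reason concerns missing data and applies to YGTSS-TTS. Relapse is loss of at least half the improvement from Day 1 to Week 12, so both scores fix the threshold, and a relapsing subject is withdrawn from blinded medication and goes to the Week 24/Relapse/ET visit. Day 1 therefore helps determine whose later scores are missing. SAP 10.2.25 justifies the model by missing at random, yet neither the model nor the imputation models in 10.2.25.1 condition on Day 1.

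At stake are the interval width of the randomized mean-change comparisons and the credibility of their missing-data assumption. The primary result is not affected.

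**Working it through.** **The plan's own figures.** The documents give no SD, correlation or power for these models. The only sizing is for Relapse (SAP 4.3), and it reproduces. Freedman's formula at hazard ratio 0.4, two-sided 0.05 and 85% power gives (1.960 + 1.036)² × (1.4/0.6)² = 48.9, so 49 events. At 65% and 34% Relapse, 49/0.495 = 99 subjects, against 98 stated.

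**Subjects available.** 98 children and adolescents plus 50% of 40 adults (assuming the same response rate) gives 118. If all relapse at the planned rates, those without Relapse at Week 24 number 59 × 0.35 + 59 × 0.66 = 59.6, about 60.

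**Gain from Day 1 in a model that already has Week 12.** Let r be the partial correlation of Day 1 with the outcome given Week 12 and treatment. As a single-time-point approximation,

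variance ratio = (1 − r²) × (ν − 1)/(ν − 2), with ν = n − 6

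The six existing coefficients are intercept, treatment, region, two for age group, and Week 12. The second factor is the cost of one more covariate: 111/110 at n = 118 and 53/52 at n = 60.

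| r (assumed) | variance ratio, n = 118 | SE ratio, n = 118 | variance ratio, n = 60 | SE ratio, n = 60 |
|---|---|---|---|---|
| 0 | 1.009 | 1.005 | 1.019 | 1.010 |
| 0.1 | 0.999 | 0.999 | 1.009 | 1.005 |
| 0.2 | 0.969 | 0.984 | 0.978 | 0.989 |
| 0.3 | 0.918 | 0.958 | 0.927 | 0.963 |
| 0.4 | 0.848 | 0.921 | 0.856 | 0.925 |
| 0.5 | 0.757 | 0.870 | 0.764 | 0.874 |

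Break-even is r = √(1 − 110/111) = 0.095 at n = 118, and √(1 − 52/53) = 0.14 at n = 60.

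**What r might be.** With correlations a (Day 1, Week 12), b (Day 1, Week 24) and c (Week 12, Week 24), r = (b − ac)/√[(1 − a²)(1 − c²)]. If all three equal ρ, this is ρ/(1 + ρ): 0.23, 0.33 and 0.41 for ρ = 0.3, 0.5 and 0.7. The variance reduction before the one-covariate cost is then 5%, 11% and 17%. If correlation decays serially, b = ac, so r = 0 and there is no gain.

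**In points.** Protocol 5.3.2 reports a difference of 3.4 and an effect size of 0.48 for the Phase 2b study, implying an SD of about 3.4/0.48 = 7.1. At 49 per arm the SE is 7.1 × √(2/49) = 1.43. It becomes 1.41 at r = 0.2 and 1.35 at r = 0.33, ignoring the small covariate cost.

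**Simulations** (118 randomized, responders only; all distributional inputs are assumptions). The table gives the empirical variance of the treatment difference with Day 1, divided by that without.

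| Setting | Variance ratio |
|---|---|
| Complete data, no drift to Day 1 | 0.97 to 1.01 |
| Complete data, 30% drift on placebo, 10% on ecopipam | 0.95 to 0.99 |
| Complete data, 60% drift on placebo, 30% on ecopipam | 0.85 to 0.91 |
| Data ending at Relapse (65%/34%), noise SD 1, 2, 3 points, 250 trials each | 0.77, 0.89, 0.97 |
| Data ending at Relapse, subject-specific return to Day 1, noise SD 1, 2, 3, 1,500 trials each | 0.94, 0.985, 0.995 |
| Data ending at Relapse, from low noise with strong drift to higher noise with visit-specific coefficients | about 0.83 to 1.0 or slightly above |

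In the fourth row the model-based ratios were 0.80, 0.87 and 0.92. A separate complete-data run with 30% placebo drift gave mean treatment estimates of −2.962 without and −2.963 with Day 1. With data ending at Relapse the estimate also changed little.

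**Relapse threshold.** Half the improvement is lost at (Day 1 + Week 12)/2. Take two subjects at 16 points at Week 12, one from 22 at Day 1 (27% improved) and one from 40 (60% improved). Their thresholds are 19 and 28. The first reaches Relapse after a 3-point rise, the second only after 12. Week 12 alone cannot distinguish them.

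**The case against.** A reader might infer that the SAP drops a covariate the protocol requires and conceals this in section 14. Under the SAP's own definition of Baseline that reading is available, but the documents do not settle it. The protocol sentence also covers change from Randomization in CaGI-C and CGI-TS-I, which have no scheduled Day 1 score, so Day 1 cannot be meant for every endpoint it governs. Reading it as the starting value of each change score fits them all, and the SAP follows that reading throughout. The protocol defers details to the SAP and never asks for both scores in one model. What remains is a gap in wording.

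A reader might also infer that precision is certainly lost. That is not shown. Week 12 is the score nearest randomization and the start of the change score, so adjusting for it is standard and valid. The largest simulated gain, 23%, needs a noise SD of 1 point. Exclusion 11 tolerates Screening-to-Baseline differences just under 25%, about 7 points at a score of 30, and the protocol describes tics as waxing and waning. With 250 trials, the ratio of 0.97 at SD 3 has a Monte Carlo interval of about 0.93 to 1.01, which includes no gain. Only YGTSS-TTS was simulated; for the other scales the gain is presumed by analogy.

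Finally, no decision depends on these models. They are outside the testing order in SAP 10.2 and do not drive the 49 events. All of this stands and limits the point's weight. It does not remove the case for using a pre-randomization score that is already collected and helps determine missingness for YGTSS-TTS.

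**Conclusion.** The point holds as a minor, optional improvement. The six SAP sections adjust for Week 12 only, and a potentially prognostic Day 1 score is available for each of their scales. The expected gain is nil to modest, roughly 0 to 20% of the variance of the treatment difference. The upper end needs low rating noise and strong drift back to Day 1. The worst case is a very small loss: about 0.5% on the standard error at 118 subjects and 1% at 60, for a single added coefficient.

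The range rests on a partial correlation, noise level and drift pattern that the documents do not give. The missing-data argument is qualitative and specific to YGTSS-TTS. It makes missing at random more plausible, but it should not be read as evidence of bias, because the simulated estimates barely moved. The endpoints are exploratory, and an undeclared protocol departure is not established.

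**What to change.** In SAP 10.2.4, 10.2.5, 10.2.6, 10.2.10, 10.2.19 and 10.2.23, add the Day 1 score of the same scale as a second covariate beside the Week 12 score. Enter it as a single main effect, as Week 12 is. Add it to the matching imputation models in 10.2.25.1 and Appendices 16.2 to 16.4, and to the analysis model in the tipping-point code. Leave CaGI-C (10.2.7) and CGI-TS-I (10.2.9) unchanged, since neither has a scheduled Day 1 score.

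State in the SAP that Week 12 is the starting-score covariate for change-from-Randomization models, which closes the ambiguity with Protocol 13.4.1.

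The cost is one degree of freedom per model and SAP wording, with no new data. The change should be made before unblinding.

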4. LIST OF ABBREVIATIONS AND DEFINITIONS OF TERMS

The following abbreviations and specialist terms are used in this study protocol:

| Abbreviations | Terms |
|----------------------|--|
| ADD | Attention Deficit Disorder |
| ADHD | attention deficit/hyperactivity disorder |
| ADL | Activities of Daily Living |
| AE | adverse event |
| AIMS | Abnormal Involuntary Movement Scale |
| ALT | alanine aminotransferase |
| AMP | adenosine monophosphate |
| AST | aspartate aminotransferase |
| ATC | Anatomic Therapeutic Classification |
| AUC | area under the plasma-concentration time course profile |
| AUC (0-24 hr) | area under the plasma-concentration time course profile from |
| , , | time 0 (dosing) to 24 hours after dosing |
| BUN | blood urea nitrogen |
| C&A-GTS-QOL | Child and Adole cent Gilles de la Tourette Syndrome-Quality |
| | of Life Scales |
| CAARS-S:S | Conners Adult ADHD Ratings Scale – Self Report: Short |
| | Version |
| CaGI-C | Car giver Global Impression of Change |
| CFR | Code of Federal Regulations |
| CDI | Children's Depression Inventory |
| CDRS-R | Children's Depression Rating Scale-Revised |
| CY-BOCS-II | Children's Yale-Brown Obsessive-Compulsive Scale-II |
| CGI | Clinical Global Impression |
| CGI-TS-I | Clinical Global Impression Tourette's Syndrome of |
| | Improvement |
| CGI-TS-S | Clinical Global Impression Tourette's Syndrome of Severity |
| C_{max} | maximum observed concentration |
| CNS | Central nervous system |
| COVID-19 | SARS-CoV-2 (coronavirus) |
| CRA | Clinical research associate |
| CRO | Clinical research organization |
| CSR | Clinical Study Report |
| C-SSRS | Columbia-Suicide Severity Rating Scale |
| CTC | Common Toxicity Criteria |
| CTCAE | Common Terminology Criteria for Adverse Events |
| CV | coefficient of variation |
| DCI | Diagnostic Confidence Index |
| DSM-5-TR | Diagnostic and Statistical Manual of Mental Disorders – |
| | 5 th Edition-Text Revision |

Emalex Biosciences, Inc. Protocol EBS-101-TD-301 Version 9.0, 05 March 2024 Ecopipam

DSMB Data Safety Monitoring Board

ECG Electrocardiogram Electroencephalogram **EEG**

Extrapyramidal Symptom Rating Scale **ESRS**

Food and Drug Administration FDA

Good Clinical Practices **GCP**

GS Global score

Gilles de la Tourette Syndrome-Quality of Life Scale **GTS-QOL**

Hamilton Rating Scale for Anxiety HAM-A

Hydrochloride HC1

(2β-carbomethoxy-3β-[4-iodophenyl]tropane) single photon 123I-β-CIT SPECT

emission computed tomography

Hemoglobin A1c HbA1c Interim analysis IA

Informed Consent Form **ICF**

International Conference on Harmonization **ICH**

Independent Ethics Committee IEC

Intramuscular IM

Investigational medicinal product **IMP** Institutional Review Board **IRB**

Intrauterine device **IUD**

IUS Intrauterine hormone-releasing system

IV Intravenous

Ki Inhibition constant LDH lacta e dehydrogenase Liv r function test(s) LFT Lesch Nyhan Disease LND

Medical Dictionary for Regulatory Activities MedDRA

National Cancer Institute NCI

Obsessive-Compulsive Disorder **OCD** Pediatric Anxiety Rating Scale **PARS**

Phencyclidine **PCP**

Positron emission tomography **PET** Patient Health Questionnaire – 9 PHQ-9

Principal Investigator PΙ

Oral (per os) PO

PUTS Premonitory Urge for Tics Scale

Once daily OD

SAE serious adverse event

SC Subcutaneous

SCH Schering-Plough drug code indicator

Swanson, Nolan, and Pelham-IV-26 questionnaire SNAP-IV-26

time from dosing to the maximum observed concentration t_{max}

Tourette's Disorder TD THC Tetrahydrocannabinol Tourette's Syndrome TS

Emalex Biosciences, Inc.Protocol EBS-101-TD-301EcopipamVersion 9.0, 05 March 2024

TTS Total Tic Score US United States

WMA World Medical Association

Y-BOCS-II Yale – Brown Obsessive-Compulsive Scale-II

YGTSS Yale Global Tic Severity Scale

YGTSS-GS Yale Global Tic Severity Scale- Global Severity YGTSS-TTS Yale Global Tic Severity Scale- Total Tic Score

Protocol EBS-101-TD-301 Version 9.0, 05 March 2024

